1.2 SCHEMA

Figure 1: ANB019-209 Study Schema

^a Study treatment will be administered according to the following schedule:

Arm 1: Imsidolimab 400 mg on Day 1, 200 mg on Days 29 and 57

Arm 2: Imsidolimab 200 mg on Day 1, 100 mg on Days 29 and 57

Arm 3: Placebo on Days 1, 29, and 57

Study treatment will be administered as 2 x 2 mL injections on Day 1 and 1 x 2 mL injection on Days 29 and 57, according to [Table 3](#).

1.3 SCHEDULE OF ACTIVITIES

The screening evaluation will only be performed after the subject has agreed to participate and has signed and dated the ICF or assent. No treatment or study-related procedures will be initiated before informed consent/assent (when applicable) is signed. The Day 1 visit must be performed, at the latest, 30 days after the screening visit.

The screening evaluation will be performed according to the inclusion and exclusion criteria. If the subject fulfills all inclusion criteria and no exclusion criteria, he or she may be included in the study.

Table 1 provides a description of the procedures to be performed at each visit during the study. Of note, the primary endpoint will be evaluated on Day 85 (Week 12).

Unless specified otherwise, the study assessments scheduled on Day 1 must be performed before study treatment administration. The specific order for performing the study assessments is as follows (applicable to all visits):

- Subject-reported questionnaires
- Efficacy assessments (global assessments [Facial IGA] **must** be performed before more quantitative assessments [lesion count])
- Physical examination
- ECG
- Vital signs
- Blood samples collection (for safety, PK, ADA)
- Photography (may be performed anytime predose provided it is before skin sample collection)
- Tape stripping

The Coronavirus Disease 2019 (COVID-19) pandemic may impact the ability to adhere to the study procedures described in **Table 1** due to challenges that include, but are not limited to, subject preferences, site closures, travel restrictions, and quarantines. Please refer to **Section 4.5** for more details on allowable, as necessary, modifications to the protocol due to COVID-19 restrictions, including conducting optional home visits when on-site study visits are considered not feasible. Such modifications in study conduct always must be in accordance with local regulations/mandates.

Efficacy and Safety of Imsidolimab in Subjects with Acne Vulgaris
Protocol ANB019-209

Version 1.0
11 February 2021

Table 1: Schedule of Activities

Study visit Window (days)	Screening Period (-30 to -1)	Treatment Period					Follow-Up Period D141 (W20) (EOS/ET) ^a (±5)
		D1	D15 (W2) (±2)	D29 (W4) (±4)	D57 (W8) (±4)	D85 (W12) (±4)	
Informed consent/assent ^b	X						
Demographics	X						
Inclusion and exclusion criteria	X	X					
Medical and surgical history	X	X					
Height and weight ^c	X	X					X X
Complete physical examination ^d	X	X		X X			X X
Vital signs ^e	X	X	X	X X	X		X X
12-Lead ECG ^f	X	X		X X		X	X X
Hematology and biochemistry ^g	X	X	X X	X X	X X	X X	X X
Urinalysis ^g	X	X		X X	X X	X X	X X
TB screening (QuantiFERON®-TB Gold test)/chest x-ray per local standard ^g	X						
Viral serology ^g	X						
FSH ^g	X						
Serum pregnancy test (WOCBP only) ^g	X						X
Urine pregnancy test (WOCBP only) ^g		X	X X	X X	X X	X X	
Facial IGA ^h	X	X	X X	X X	X X	X X	X X
Facial inflammatory/noninflammatory lesion count ^h	X	X	X X	X X	X X	X X	X X
Truncal (chest, neck, and back) PGA ^h	X	X	X X	X X	X X	X X	X X
PGIS ^h	X	X	X X	X X	X X	X X	X X
PGIC ^h			X X	X X	X X	X X	X X
DLQI/CDLQI ^h		X	X X	X X	X X	X X	X X
SSQ ^h		X	X X	X X	X X	X X	X X
SSRS ^h						X X	X X
Photography	X	X	X X	X X	X X	X X	X X
Blood samples for PK ⁱ		X	X X	X X	X X	X X	X X
Blood samples for ADA		X	X X	X X	X X	X X	X X
Tape strip collection ^j		X		X X		X X	
Randomization		X					
Study treatment administration ^k		X		X X	X X		
AE/SAE review	X			Continuously			
Concomitant medication review ^l	X			Continuously			

Efficacy and Safety of Imsidolimab in Subjects with Acne Vulgaris
Protocol ANB019-209

Version 1.0
11 February 2021

Table 1: Schedule of Activities (continued)

Abbreviations: ADA, anti-drug antibody; AE, adverse event; CDLQI, Children's Dermatology Life Quality Index; D, day; DLQI, Dermatology Life Quality Index; ECG, electrocardiogram; EOS, end of study; ET, early termination, FSH, follicle-stimulating hormone; IGA, Investigator's Global Assessment; PGA, Physician's Global Assessment PGIC, Patient Global Impression of Change; PGIS, Patient Global Impression of Severity; PK, pharmacokinetic; SAE, serious adverse event; SC, subcutaneous; SoA, Schedule of Activities; SSRS, Subject Satisfaction Rating Scale; SSQ, Subject Satisfaction Questionnaire; TB, tuberculosis; W, week; WOCBP, woman of childbearing potential.

- ^a The ET visit will include all procedures to be done at the EOS visit (Day 141 [Week 20]).
- ^b Adolescent subjects who reach 18 years of age during the study must be reconsented as adults.
- ^c Height will be measured at screening only. Subjects below the age of 18 at the start of the study will have height measured at Week 12.
- ^d Refer to [Section 8.2.3](#) for details regarding the complete physical examination.
- ^e Refer to [Section 8.2.4](#) for details and instructions regarding vital signs.
- ^f Refer to [Section 8.2.5](#) for details and instructions regarding the ECG. In addition to the time points specified in the SoA, ECGs may be performed at any time during the study if, in the opinion of the Investigator, it is clinically warranted.
- ^g If a negative QuantiFERON®-TB Gold test result was obtained within 6 months of screening, it can be skipped at screening. A chest X-ray will be administered per local standards, as required. The FSH testing is performed for women not of childbearing potential (postmenopausal women with at least 12 months of amenorrhea without an alternative medical cause). An adolescent subject who experiences menarche during the trial will be considered a WOCBP (refer to [Appendix 1](#) for definition of WOCBP) and will be required to follow the contraceptive guidance in [Appendix 1](#) and undergo scheduled pregnancy testing. Additional pregnancy testing may be performed whenever a menstrual cycle is missed or when pregnancy is otherwise suspected. Refer to [Appendix 10](#) for instructions regarding clinical laboratory parameters.
- ^h Refer to [Section 8.1](#) for details and instructions regarding facial lesion count, facial IGA, truncal (chest, neck, and back) IGA, PGI-S, PGI-C, DLQI (subjects \geq 16 years of age)/CDLQI (subjects $<$ 16 years of age), SSQ, and SSRS. Facial IGA must be performed before facial lesion count.
- ⁱ On Day 1, samples for PK will be collected at predose and 2 hr (\pm 10 min) post SC administration. See [Table 5](#).
- ^j Tape stripping will be performed for all randomized subjects as part of this study (not optional). Tape strips will be collected from non-lesional and lesional skin at Day 1 and Week 12 and from lesional skin at Week 4.
- ^k During the treatment period, subjects will receive either imsidolimab or placebo SC administered as follows: 400 mg imsidolimab, 200 mg imsidolimab, or placebo on Day 1; followed by 200 mg imsidolimab, 100 mg imsidolimab, or placebo on Days 29 and 57.
- ^l At screening, prior medications should be reviewed and documented. Refer to [Section 6.5](#).

2 INTRODUCTION

2.1 STUDY RATIONALE

Acne vulgaris is a chronic dermatological condition that can result from a multitude of triggers including genetics, hormones, infections, and lifestyle, and is one of the most commonly occurring conditions in the world (Bhate 2013). Ongoing and severe acne can reduce quality of life, result in scarring, and have significant psychological impacts. The various triggers frequently result in proliferation of *Propionibacterium acnes* (*P. acnes*), which further elicits an inflammatory response in and around the pilosebaceous unit resulting in lesions (comedones, papules, pustules, nodules) (Dreno 2017; Suh 2015).

The inflammatory response in patients with acne has been shown to involve a variety of cytokines/receptors including TNF α , various interleukins, and MMPs. Di Caprio et al. (2017) conducted a biopsy-based assessment of IL-36Ra and IL-36 cytokine expression in lesional samples from subjects with AV and found that subjects with AV had significantly elevated expression of IL-36 cytokines, but not IL-36Ra, relative to controls. IL-36Ra is known to inhibit the effects of Interleukin-36 cytokines (IL-36 α , IL-36 β and IL-36 γ) via competing with their receptor IL-36R and thereby inhibiting their proinflammatory effects. Additionally, it was shown that IL-36Ra expression was negatively correlated with IL-8 expression. This is consistent with previous investigations demonstrating IL-36-mediated induction of IL-8 expression (Carrier 2011). Abd El All et al. (2007) assessed IL-8 expression in skin biopsies from lesional and nonlesional skin in 29 subjects and found that lesional skin had significantly increased IL-8 expression compared to nonlesional skin. Furthermore, IL-8 expression was shown to be associated with increased inflammatory infiltrates in the dermis. In vitro, Nagy et al. (2005) co cultured human keratinocytes with four different strains of *P. acnes* and found that all four strains resulted in significantly elevated IL-8 mRNA expression, indicative of a potential inflammatory response. In sum, AV is associated with multifactorial triggers which result in an inflammatory response leading to various lesions.

Imsidolimab is a high affinity, humanized immunoglobulin G4 (IgG4) monoclonal antibody (mAb) that specifically binds IL-36 receptor (IL-36R) and antagonizes IL-36 signaling. The IL-36 cytokines (IL-36 α , IL-36 β , and IL-36 γ) engage with IL-36R to initiate signaling events leading to proinflammatory responses. IL-36 signaling is counterbalanced by IL36Ra. Because the IL-36 pathway has been implicated in amplifying inflammatory skin diseases, inhibition of IL-36 signaling, by targeting IL36R with a specific mAb, may represent a novel strategy to control the pathological inflammatory cascade driven by IL-36 pathway activation. Imsidolimab is currently being studied as a potential first-in-class therapy for several cutaneous indications, including generalized pustular psoriasis (GPP), palmoplantar pustulosis (PPP), ichthyosis, hidradenitis suppurativa, and other inflammatory diseases in which the IL-36 pathway may play

Efficacy and Safety of Imsidolimab in Subjects with Acne Vulgaris
Protocol ANB019-209

Version 1.0
11 February 2021

a significant role in augmenting the disease. Imsidolimab may be beneficial in suppressing the inflammation in patients with AV.

2.2 BACKGROUND

2.2.1 NONCLINICAL STUDIES

Imsidolimab exhibits strong inhibitory activity for human as well as cynomolgus monkey IL36R (cyIL-36R) cell populations. Nonclinical data obtained from studies with imsidolimab in primary human and cynomolgus monkey cells and from *in vivo* nonhuman primate studies demonstrated that imsidolimab shows reactivity with human and cynomolgus monkey IL36R (dissociation constant [K_D] of 67.9 ± 31.4 pM and 80.0 ± 49.6 pM, respectively), but not with mouse or rat IL-36R.

In primary human and cynomolgus monkey cell populations, keratinocytes, peripheral blood mononuclear cells (PBMCs), and human whole blood, imsidolimab inhibited IL-36R mediated release of IL-8.

The terminal half-life ($t_{1/2}$) of imsidolimab in cynomolgus monkeys was 304 hr after single intravenous (IV) dose administration, and 310 hr after a single SC dose administration at 10 mg/kg, with bioavailability approximately 76% consistent with the anticipated PK characteristics for a human IgG4 scaffold mAb in the cynomolgus monkey.

Repeat-dose, Good Laboratory Practice (GLP) toxicity and toxicokinetic (TK) studies of 4, 13, and 26 weeks in duration have been conducted with imsidolimab administered by weekly SC and IV injection in cynomolgus monkeys. There were only minor treatment-related injection site findings in the 4-week repeat-dose study. Treatment-related effects in the 13-week toxicity study included increased observations of nonformed feces and prolapsed rectum, and protozoa in the stomachs of cynomolgus monkeys; the latter being consistent with the mechanism of action of an immune-modulator in cynomolgus monkeys ([Dubey 2002](#)). Weekly administrations of vehicle control article, 30 mg/kg/dose imsidolimab via SC injection, or 60 mg/kg/dose imsidolimab via SC or IV bolus injection, to male and female sexually mature cynomolgus monkeys during the 26-week toxicity and TK study was well tolerated. Imsidolimab-related effects were limited to a low incidence of liquid feces not considered AEs for animals administered 60 mg/kg/dose IV. Thus, the no observed adverse effect level (NOAEL) is 60 mg/kg/dose administered by SC or IV injection. These data provide a strong scientific rationale for advancing imsidolimab through clinical development.

A detailed description of the physical, chemical, and pharmaceutical properties of imsidolimab and nonclinical studies is provided in the Investigator's Brochure (IB).

2.2.2 CLINICAL STUDIES

Currently, two Phase 1 clinical studies (ANB019-001 and ANB019-005) have been completed. Study ANB019-001 was a Phase 1, first-in-human, single ascending dose (SAD) and multiple ascending dose (MAD) study in healthy volunteers and in subjects with psoriasis. Study ANB019-005 was a Phase 1, ethno-bridging study, a single-dose safety, tolerability, PK, and immunogenicity study of imsidolimab in healthy Japanese and Caucasian subjects. A detailed description of the safety and tolerability, and PK/pharmacodynamic (PD) results of these two Phase 1 clinical studies is provided in the IB.

In addition, four Phase 2 studies (ANB019-002, ANB019-003, ANB019-206 and ANB019-207) to evaluate clinical activity and safety of imsidolimab in GPP, PPP, ichthyosis, and EGFRi/MEKi related acneiform rash, respectively, are ongoing. Study ANB019-002 is a single-arm, multiple-dose study to be conducted in subjects with active GPP. Study ANB019-003 is a randomized, placebo-controlled, multiple dose study to be conducted in subjects with PPP. Study ANB019-206 is a randomized, placebo-controlled, multiple dose study to be conducted in adolescent and adult subjects with ichthyosis. Study ANB019-207 is a randomized, placebo-controlled, multiple dose study to be conducted in subjects with acneiform rash resulting from treatment with EGFRi/MEKi therapy.

2.3 RISK/BENEFIT ASSESSMENT

2.3.1 KNOWN POTENTIAL RISKS

No major toxicities were observed in the 4-week repeat-dose toxicity study in cynomolgus monkeys. The main finding consisted of minor, injection site reactions associated with the SC route of administration and not considered AEs.

In cynomolgus monkeys, treatment-related effects observed in the 13-week repeat-dose toxicity study included protozoa in the stomach, an increase in nonformed feces and prolapsed rectum observations; the latter observation was not considered dose related. The increase in protozoa in the stomach has been observed in monkeys treated with immune-modulating drugs (Dubey 2002) and is consistent with the putative mechanism of action of imsidolimab. During the 26-week repeat-dose toxicity study, imsidolimab-related effects were limited to a low incidence of liquid feces. In the monkeys, the increased incidence of protozoa, nonformed feces, and prolapsed rectum were not considered AEs as they responded to veterinarian intervention. In humans, gastrointestinal infections can be clinically monitored and, in the case of most protozoa, are readily treatable even in the context of immunocompromised individuals (Farthing 2006).

One female monkey receiving 60 mg/kg imsidolimab IV was found moribund on Study Day 34. The cause of death was not determined and had an uncertain relationship to imsidolimab but

Efficacy and Safety of Imsidolimab in Subjects with Acne Vulgaris
Protocol ANB019-209Version 1.0
11 February 2021

could be due to treatment-related immune modulation. However, data published on IL-36R deficient humans shows no deleterious effect on general health, and normal immune function is broadly preserved, indicating that inhibition of IL-36R, does not generally compromise host defenses. Similar to other immune-modulating treatment paradigms, subjects should be closely monitored for any clinical gastrointestinal manifestations including infections and evaluated on an ongoing basis. If a gastrointestinal infection is suspected, the subject should be treated as clinically indicated.

In the ANB019-001 study in healthy adults, single doses of imsidolimab up to 750 mg administered by IV infusion or SC injection to 32 healthy adults in the SAD part of the Phase 1 study were generally well tolerated with a similar number of treatment-emergent adverse event (TEAEs) reported in subjects receiving imsidolimab or placebo, 29 subjects (81%) and 11 subjects (92%), respectively. The most frequently reported AEs were upper respiratory tract infection (URTI; 10 [28%] imsidolimab; 6 [50%] placebo), headache (10 [28%] imsidolimab; 3 [25%] placebo), and viral URTI (4 [11%] imsidolimab; 1 [8%] placebo). Additionally, multiple doses of imsidolimab up to 300 mg administered by IV infusion once weekly for 4 weeks to 18 healthy adults were also well tolerated. Overall, TEAEs occurred in 16 subjects (89%) receiving imsidolimab and in 3 subjects (50%) receiving the placebo. The most common AEs were headache (7 [39%] imsidolimab; 1 [17%] placebo) and URTI (3 [17%] imsidolimab; 1 [17%] placebo).

In ANB019-005, single doses of imsidolimab up to 750 mg administered by IV infusion or SC injection to 32 healthy Japanese and Caucasian adults were generally well tolerated. The most common TEAEs were alanine aminotransferase (ALT) increased (3 subjects [9.4%]) and aspartate aminotransferase (AST) increased (2 subjects [6.3%]).

One SAE of sepsis was reported in the ongoing ANB019-002 study in subjects with GPP; the SAE was considered possibly related to the study drug. The subject had a medical history of sepsis and experienced the SAE after the 750 mg IV dose administration. Antibiotic treatment rapidly resolved the sepsis episode with complete subject recovery. Further details of imsidolimab clinical studies are in the IB.

As allergic or anaphylactic reactions may occur in any subjects treated with mAbs, subjects should be observed during study drug administration and for a period of 2 hr after study drug administration. Subjects with true allergic/anaphylactic reactions should not receive further doses of the monoclonal antibody. Symptoms of an apparent allergic reaction to the drug, also known as ‘cytokine release syndrome’, vary dramatically but can include:

- Mild to moderate fever, chills, headache, nausea, and vomiting
- Moderate to severe symptoms such as edema, hypotension, and pulmonary infiltrates (eg, blood and mucus in the lung)

Efficacy and Safety of Imsidolimab in Subjects with Acne Vulgaris
Protocol ANB019-209

Version 1.0
11 February 2021

Such reactions should be managed as clinically indicated and according to standard clinical practice.

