6.1.2 DOSING AND ADMINISTRATION

Study treatment dosing and administration details are provided in [Table 2](#). Further information will be provided in the Pharmacy Manual.

Table 2: Study Treatment Details

Study Treatment Name:	Imsidolimab (ANB019) Anti-interleukin 36 receptor monoclonal antibody	Placebo
Dosage Form:	Solution for injection	
Source of procurement:	AnaptysBio, Inc.	
Study Treatment Description	Imsidolimab will be provided as a sterile, colorless to yellow, and clear to slightly opalescent solution supplied in a single use, 2R, Type I glass vial with a fill volume of 1.2 mL. Each vial contains 120 mg of imsidolimab at a concentration of 100 mg/mL.	The placebo contains no active ingredient and will be provided as a sterile, colorless to slightly yellowish, and clear to very slightly opalescent solution supplied in a single use, 2R, Type I glass vial with a fill volume of 1.2 mL.
Dosage Formulation:	100 mg/mL imsidolimab in 25 mM-histidine, 60 mM-NaCl, 145 mM sorbitol, and 0.02% v/v polysorbate-20 at pH 6.0.	Placebo (25 mM-histidine, 60 mM-NaCl, 145 mM sorbitol, and 0.02% v/v polysorbate-20, at pH 6.0).
Unit Dose Strength(s)/ Dosage Level(s):	Study treatment will be administered as 400/200/100 mg of imsidolimab or placebo. 1 mL vials of active and placebo doses will be provided to sites and prepared by an unblinded pharmacist according to Table 3 .	
Route of Administration:	SC injection (3 doses during the treatment period)	
Dosing Instructions:	Imsidolimab and placebo should be administered by clinic staff trained in best practices for SC administration of study treatments.	

Efficacy and Safety of Imsidolimab in Subjects with Acne Vulgaris
Protocol ANB019-209

Version 1.0
11 February 2021

Study Treatment Name:	Imsidolimab (ANB019) Anti-interleukin 36 receptor monoclonal antibody	Placebo

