	
For SC injections, imsidolimab and placebo should be prepared by drawing up the required dosing volume into suitable sized syringe and attaching a dosing needle. No further dilution is required. Syringes should be covered in tape by an unblinded pharmacist to obscure color and volume.
 
The preferred anatomical site of SC administration is the abdomen; however, the injection may be made in the upper arm, if needed.
 
A 30-minute observation period should be included after the first dose administered.
 
The same anatomical site should be used throughout the entire study for a given subject (ie, do not administer one dose into the upper arm and at a subsequent visit or dose, administer the next dose into the abdomen).
 
Subsequent doses should be rotated within an anatomical site (ie, if the upper left abdominal quadrant is used as the initial site of administration, then the next administration at a subsequent visit should be rotated to the upper right quadrant).
 
Subcutaneous injections should not be given into moles, scars, tattoos, or areas where the skin is tender, bruised, red, hard, or not intact.
 
Prior to SC needle insertion, the skin will be pinched between the thumb and index finger to separate the subcutaneous layer from the muscle.
 
The needle is to be injected at a 90-degree angle to the fat pad.
 
The plunger will be pressed gently until the entire dose is delivered to the SC space and the needle will be held in place (fully depressed) for 10 seconds after the injection is administered.
 
The needle will be removed and then the skin pinch released; any leakage or backflow of fluid from the administration site onto the surface of the skin will be noted and documented in the eCRF.
 
The site of administration is NOT to be massaged by either the clinic staff or by the subject for at least 60 minutes after drug administration.
	

Abbreviations: eCRF, electronic case report form; NaCl, sodium chloride; SC, subcutaneous.

The contents of the label will be in accordance with all applicable regulatory requirements.

Efficacy and Safety of Imsidolimab in Subjects with Acne Vulgaris
Protocol ANB019-209

Version 1.0
11 February 2021

Table 3: Treatment Administration Schedule

Arm	Day 1 2 x 2 mL ^a	Weeks 4 and 8 1 x 2 mL ^a
1 (400mg/200mg)	2 x 2 mL imsidolimab	1 x 2 mL imsidolimab
2 (200mg/100mg)	1 x 2 mL imsidolimab 1 x 2 mL placebo	1 x 2 mL [imsidolimab (1 mL): placebo (1 mL)]

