8 STUDY ASSESSMENTS AND PROCEDURES

Study procedures and their timing are summarized in the SoA ([Section 1.3](#)). Assessments scheduled on the day of study treatment administration must be performed prior to the study treatment administration unless otherwise noted. There are visits where the protocol requires more than 1 procedure to be completed at the same time point. When indicated, the procedures must follow the specific order of events; see [Section 1.3](#) for instructions.

Protocol waivers or exemptions are not allowed.

Immediate safety concerns should be discussed with the Medical Monitor immediately upon occurrence or awareness to determine if the subject should continue or discontinue in the study.

Adherence to the study design requirements, including those specified in the SoA, is essential and required for study conduct.

All screening evaluations must be completed and reviewed to confirm that potential subjects meet all eligibility criteria. The Investigator will maintain a screening log to record details of all subjects screened and to confirm eligibility or record reasons for screening failure, as applicable.

Procedures conducted as part of the subject's routine clinical management (eg, blood count) and obtained before signing of the ICF may be utilized for screening purposes provided the procedures met the protocol specified criteria and were performed within the time frame defined in the SoA ([Section 1.3](#)).

Repeat or unscheduled samples may be taken for safety reasons or for technical issues with the samples.

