8.3.2 PHARMACOKINETICS

Whole blood will be obtained for the determination of imsidolimab concentration in human serum. Samples will be collected according to the SoA ([Section 1.3](#)) and [Table 5](#). Whole blood will be obtained from each subject for PK assessments during the study. Each serum sample will be divided into 2 aliquots (1 each for primary and a back-up). Samples collected for analyses of imsidolimab serum concentration also may be used to correlate exposure to safety or efficacy as well as supportive analysis for dose justification.

The actual date and time (24-hour clock) of the blood sample collection will be recorded in the subject's eCRF. The details of blood sample collection, sample tube labeling, sample preparation, storage, and shipping procedures will be described in a separate laboratory manual.

The measurement of the concentrations of imsidolimab will be performed using a validated assay method under the supervision of AnaptysBio. The analytical methods used to measure concentrations of imsidolimab will be described in a separate bioanalytical report.

Only samples within the stability window of the assay will be analyzed.

While PK samples must be collected from subjects randomized to the placebo arm to maintain the blinding of treatment assignment, PK assay results for these subjects are not needed for the safe conduct or proper interpretation of this study. These samples may not be analyzed unless needed to investigate if a dosing error has occurred. Personnel at the bioanalytical laboratory performing PK assays will be unblinded, the clinical study team members, and study site staff (with the exception of the unblinded Pharmacist) will remain blinded to treatment for the duration of the study. Data may be de-identified for quality review. Additional details on de-identification or unblinding of the PK data, if applicable, will be described in a separate plan.

Drug concentration information that may unblind the study will not be reported to study sites or blinded personnel until the study has been unblinded.

Table 5: Pharmacokinetic and Anti-drug Antibody Collection Schedule

Study Visit	PK Sample Time Point	ADA Sample Time Point
Day 1	Predose	Predose
	2 hr (\pm 10 min) postdose	
Day 15	Anytime	Anytime
Day 29	Predose	Predose
Day 57	Predose	Predose
Day 85	Anytime	Anytime
Day 141	Anytime	Anytime

Abbreviations: ADA, anti-drug antibody; hr, hours; min, minutes; PK, pharmacokinetic

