## 3. STUDY DESIGN

### 3.1 Study Design

This is a Phase 2, multicenter, randomized, double-blind, placebo-controlled study to evaluate the efficacy and safety of imsidolimab in adolescent and adult subjects with AV. This study also will characterize the pharmacokinetic (PK) profile of imsidolimab and explore the immune response to imsidolimab in subjects with AV. This study will be conducted at approximately 15 sites, contributing approximately 8-12 subjects per site. Approximately 120 adult male and female subjects, aged 12 to 45 years with clinically confirmed diagnosis of AV will be enrolled in this study. At the screening and Day 1 visits, the subjects will need to have a facial Investigator Global Assessment (IGA) score of 3 (moderate) or 4 (severe), at least 20 and no more than 100 inflammatory lesions on the face, no more than 100 noninflammatory lesions on the face, and no more than 5 nodules ( $\geq 5$  mm) on the face. Eligible subjects

will be randomized (1:1:1) to receive either imsidolimab (at 1 of 2 different regimens) or placebo, subcutaneously (SC) administered on 3 occasions: Day 1, Day 29 (Week 4), and Day 57 (Week 8). The randomization will be stratified based on facial IGA score at baseline (3 [moderate] vs. 4 [severe]). The maximum study duration per subject is approximately 24 weeks, which includes a screening period of up to 30 days followed by a 12-week treatment period and an 8-week safety follow-up period.

The overall study design is summarized and illustrated in **Figure 1**.

Abbreviations: D, day; SC, subcutaneously; W, week.

a Study treatment will be administered according to the following schedule:

Arm 1: Imsidolimab 400 mg on Day 1, 200 mg on Days 29 and 57

Arm 2: Imsidolimab 200 mg on Day 1, 100 mg on Days 29 and 57

Arm 3: Placebo on Days 1, 29, and 57

Study treatment will be administered as 2 × 2 mL injections on Day 1 and 1 × 2 mL injection on Days 29 and 57, according to Protocol [Table 3](#).

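### Post-dose observation is 2 hr in Protocol Section 2.3.1 but 30 minutes, first dose only, in the Table 2 dosing instructions; the two should be aligned

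*Protocol*

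**What the plan says.** Two parts of the current protocol set an observation period after injection.

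- **Section 2.3.1 (Known Potential Risks)** notes that any subject given a monoclonal antibody may have an allergic or anaphylactic reaction, and therefore that "subjects should be observed during study drug administration and for a period of 2 hr after study drug administration". It names no particular dose, so it covers all three.
- **Table 2 in Section 6.1.2 (Dosing Instructions)** says: "A 30-minute observation period should be included after the first dose administered". It is silent on the second and third doses.

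Section 6.1.2 points staff to Table 2: "Study treatment dosing and administration details are provided in" that table, with more to follow in the Pharmacy Manual. Table 2 is otherwise detailed. It covers needle angle, how long to hold the needle in place, and a rule that the injection site is "NOT to be massaged by either the clinic staff or by the subject for at least 60 minutes after drug administration". It does not carry or cite the 2-hr rule.

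Footnote k of the Schedule of Activities (dosing), Section 7.1.2 (re-challenge) and the home-dosing bullet in Section 4.5 give no observation time. Nor does the SAP.

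**The concern.** At dose 1 the protocol gives two different times for the same safety measure, and a general duty to follow the protocol does not tell a site which one applies.

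At doses 2 and 3 there is no contradiction, because Section 2.3.1 stands alone. The weakness is its location: the rule is in the risk section and absent from the table that staff are told to use when dosing. Someone working from Table 2 would see a shorter period at dose 1 and none afterwards.

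What is at stake is the sponsor's own safeguard against anaphylaxis, in a trial that enrols subjects from age 12, allows dosing at home by a nurse, and allows treatment to be restarted after an interruption for an adverse event. This is a subject-safety point. It does not touch sample size, power, type I error or the primary analysis.

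**Working it through.** The plan has no statistical figure to reproduce here. The check compares the texts dose by dose, asks whether anything else in the schedule fills the gap, and counts the doses involved.

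**1. Stated post-dose observation**

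| Dose | Section 2.3.1 | Table 2 | Difference on paper |
|---|---|---|---|
| Day 1 | 120 min | 30 min | 120 − 30 = 90 min |
| Day 29 | 120 min | none stated | 120 min |
| Day 57 | 120 min | none stated | 120 min |
| Total | 360 min | 30 min | 330 min |

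**2. Does another procedure keep the subject on site?**

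- *Day 1: largely yes.* Footnote i of the Schedule of Activities states: "On Day 1, samples for PK will be collected at predose and 2 hr" after injection, with a window of ±10 minutes. Placebo subjects are included, since Section 8.3.2 begins its explanation with "While PK samples must be collected from subjects randomized to the placebo arm to maintain the blinding of treatment assignment". The sample falls at 120 ± 10 = 110 to 130 minutes. A subject who waits on site for a sample taken in its window is therefore present for at least 110 minutes, leaving at most 120 − 110 = 10 minutes uncovered. The sample is a blood draw and not an observation rule.
- *Days 29 and 57: no.* Table 5 lists the PK and anti-drug antibody samples on both days as predose. Section 8 adds: "Assessments scheduled on the day of study treatment administration must be performed prior to the study treatment administration unless otherwise noted". Table 2's 60-minute no-massage rule does not ask the subject to stay.
- *Re-challenge and home doses: no observation time is stated* in Section 7.1.2 or Section 4.5.

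**3. How many doses could be involved?**

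Inputs: SAP Section 3.1 says "This study will be conducted at approximately 15 sites, contributing approximately 8-12 subjects per site"; each subject has two doses after the first; allocation is 1:1:1 with two active arms; Protocol Section 9.2 assumes that 10% discontinue before Week 12.

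For one site whose staff work from Table 2 alone:

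- Later doses = subjects × 2: 8 × 2 = 16 to 12 × 2 = 24.
- Expected active doses = later doses × 2/3: 16 × 2/3 = 10.7 to 24 × 2/3 = 16, so about 11 to 16. Randomization is stratified by facial IGA and not by site, so these are averages; the split at any one site will vary.
- If the 10% discontinuation all fell before dose 2: 16 × 0.9 = 14.4 to 24 × 0.9 = 21.6, so about 14 to 22.

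The protocol synopsis gives about 12 centers for about 120 subjects. That is 120 / 12 = 10 subjects and 10 × 2 = 20 later doses per site, inside the same range.

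These are counts of doses, not of reactions. The documents give no reaction rate and no information on how sites would behave.

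**The case against.** The strongest reply is that the practical gap is small where the texts differ, and the texts do not differ where the gap could be larger. At dose 1 a site that observes for 2 hr also satisfies the 30-minute instruction, and the PK sample keeps the subject on site for nearly all of that time. At doses 2 and 3 the 2-hr rule is binding and unopposed, and the protocol requires adherence, so the complaint there is about layout.

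Other safeguards also exist: exclusion criterion 15 on drug allergy, no further doses after a true allergic reaction, Medical Monitor discussion before a restart, permanent withdrawal after a positive re-challenge, and COVID-19 mitigation in separate study plans. The Pharmacy Manual, which was not available for this review, may add guidance. Nor do the documents show which period the sponsor intended.

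Much of this stands. Table 2 does not permit early departure at later doses, and there is no evidence that sites would overlook Section 2.3.1. But none of the listed safeguards states an observation time, a manual cannot remove two conflicting sentences from the protocol, and the PK draw exists only on Day 1. The uncertainty about intent is a reason to let the sponsor choose the period, not to leave two.

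**Conclusion.** The point holds and should be fixed. The protocol gives two observation periods for the same safety purpose, and nothing in the protocol or SAP reconciles them.

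- **Dose 1:** a direct mismatch of 90 minutes on paper, at most 10 minutes in practice for a subject who waits on site for the PK sample.
- **Doses 2 and 3:** no contradiction, but the only rule is missing from the table that governs dosing. A site working from Table 2 alone would give about 16 to 24 later doses with no stated observation period, about 11 to 16 of them active on average. The number affected could be zero.

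Confidence in the textual mismatch is high; its consequence cannot be estimated from the documents. The counts rest on the SAP's figure of 8 to 12 subjects per site and on the condition that staff use Table 2 alone.

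**What to change.** Replace the 30-minute sentence in Table 2 with the Section 2.3.1 rule: observe the subject during every dose and for 2 hr after it, whether on site or at home. Repeat it in footnote k of the Schedule of Activities and in the home-dosing bullet of Section 4.5.

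If the sponsor intends a shorter period for some doses, state it dose by dose in Table 2 and amend Section 2.3.1 to match. A cross-reference from Table 2 to Section 2.3.1 would cover doses 2 and 3, but alone it would leave the 30-minute sentence in conflict at dose 1.

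**Cost.** This is a wording change made as a protocol amendment. It needs IRB/EC review (Statement of Compliance) and any other approvals that apply under Section 10.2.2. Compared with Table 2 alone, visits on Days 29 and 57 could each be up to 2 hr longer, 2 × 2 = 4 hr per subject, with a matching longer nurse stay for home doses. Day 1 adds little for a subject already waiting for the PK sample. Compared with Section 2.3.1 as written, no time is added.
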